### 10.3 Reference test

The literature review confirmed invasive urodynamics (also known as filling and voiding cystometry) as the most appropriate diagnostic reference test for this study. The test involves passing a thin catheter into the patient's bladder, via the urethra, and another into the rectum, to measure intravesical and abdominal pressure respectively. Abdominal pressure is subtracted from intravesical pressure to give the pressure generated by the detrusor (bladder) muscle itself. Before commencing the test quality control checks are carried out including checking that pressure measurement is standardised by zeroing against atmospheric pressure; ensuring efficient subtraction of the abdominal pressure from the bladder pressure and ensuring that the detrusor (subtracted) pressure trace starts at zero. The detrusor pressure is then measured whilst the bladder is artificially filled with saline. During this time the bladder may show isolated (phasic) pressure rises diagnostic of detrusor overactivity. Once the patient's bladder is full, he passes urine into a flowmeter which measures urine volume and flow rate. Residual urine is measured at the end by ultrasound. Variables of interest

include detrusor pressure during filling ( $P_{det}$ ), maximum urine flow rate ( $Q_{max}$ ), detrusor pressure at the point of maximum flow ( $P_{detQmax}$ ), voided volume ( $V_{void}$ ) and residual volume. All these measurements are read directly from the cystometric or flow recording. Using these measurements urodynamics defines the presence or absence of three conditions: detrusor overactivity during filling, and bladder outlet obstruction and detrusor underactivity during voiding [6]. Absence of these three diagnoses will classify the individual as having normal urodynamics. The three conditions, which can co-exist, have definitions standardised by the International Continence Society [6,7] as follows:

*Detrusor overactivity:* A urodynamic observation characterised by involuntary detrusor contractions during the filling phase which may be spontaneous or provoked and which are signified by a phasic (transient) detrusor pressure rise during bladder filling associated with a sensation of urgency

*Bladder outlet obstruction:*  $P_{detQmax} - 2Q_{max} > 40$  (bladder outlet obstruction index; BOOI)

*Detrusor underactivity:*  $P_{detQmax} + 5Q_{max} < 100$  (bladder contractility index; BCI)

*Nocturnal polyuria:* It is defined as a night-time urine volume output that is > 33% of that during the whole of a respective 24-hour period [4]. This will be separately flagged up as an additional identified relevant condition using variables from the frequency/volume chart.

#### **10.4 Compliance**

A monitoring plan to assess compliance of the reference urodynamic testing will be in place. In summary, the data for the first 4 participants in each hub will be reviewed, followed by 1 in 5 for the next 25 participants in each hub. Monitoring of urodynamic test will then be conducted for every 10%. The data will be reviewed by the urologist(s) and clinical scientists on the research team. Any discrepancies will be reviewed and further training conducted.

## **11 Study Procedures**

All participants will be enrolled in the study for up to 6 months, from baseline to 6 month post-clinical assessments.

Patients will either present to their GP in an initial GP consultation visit with one or more bothersome LUTS, or they will be identified through database searches and invited to take part in the study.

### **Patients presenting to their GP with one or more bothersome LUTS**

Patients initially presenting to their GP with one or more bothersome LUTS, will be assessed for eligibility and provided with a patient information pack (i.e Patient Information Sheet, Patient

Information Leaflet, Consent Form, Urodynamics Leaflet and Frequency Volume Chart). The right of the patient to refuse consent without giving reasons will be respected throughout the study. Furthermore, the patient will be free to withdraw from the study at any time without giving reasons and without prejudicing further treatment.

The GP will follow NICE guidelines (<http://www.nice.org.uk/guidance/cg97>) and will complete the following index tests:

- Physical Examination
- Digital Rectal Examination (DRE)
- Prostate Specific Antigen (PSA) Test

The GP will complete and sign the Patient Eligibility Checklist, confirming the patient has met the criteria to enter the study. The GP can consent the patient within the initial visit, if they feel that this is appropriate. Otherwise, the potential participant will be required to complete and sign the Consent to Contact Form, confirming they are happy to be contacted by the research nurse and ensuring the responsible research nurse has their up to date contact details.

The GP will then pass the two documents to the site research nurse, to ensure they have the contact details needed to telephone the potential participant and confirmation of the patient's eligibility. GPs will also complete and sign the Patient Eligibility Results Form, documenting the results of the three index tests conducted in the initial consultation.

The participant will be given adequate time to consider taking part in the study, before being invited to attend a Study Visit (Part A and B). A research nurse will then call the potential participant, using contact details from the Consent to Contact Form and establish whether they would like to enter the study. If the potential participant agrees to enter the study during the phone call with the research nurse, they will arrange a Study Visit date. The research nurse will also instruct the patient to complete the Frequency Volume Chart, for at least 3 days, to record the volumes and timing of urine passed. prior to their Study Visit, Part A. If the potential participant decides not to enter the study, the research nurse will ask the potential participant whether they would be interested in having an informal interview. If this is something the patient is willing to consider, the research nurse will arrange to send out the separate qualitative patient information pack (including the Patient Information Sheet and Consent Form) to the potential participant. This will include a self-addressed envelope to send their completed consent form back to the research team.

#### **Patient identified by Database Searches**

Patients identified through a database search will be sent a letter from their GP (PriMUS Potential Participant Letter), informing the patient of the study and inviting them to take part. These patients will be provided with the Patient Information Summary Leaflet and the details of their local research nurse to contact, if they are interested in entering the study.

### **Study Visit**

The Study Visit can be separated into two parts, Part A and Part B. Part A and Part B can either be completed on the same day, or separated into two separate visits.

#### **Part A**

During Part A, the patient will be asked to sign the consent form (unless already been consented during the initial GP consultation). They will complete the ICIQ – Males LUTS Symptom Questionnaire and the IPSS questionnaire. The research nurse will complete the remaining index tests by completing the corresponding CRFs.

#### **Part B**

Part B, will be dedicated to completing the reference test (urodynamics). Following completion of this procedure, research nurses will appropriately debrief the patient, providing the patient with the Post Urodynamic Leaflet and Patient Safety Card, answering any questions the patient may have.

The patients will also be provided with a uroflowmetry device (home flow meter) (Flowtaker, <http://www.laborie.com/products/flowtaker/>), along with specific instructions for how to use this at home. The research nurse will instruct the patient not use the uroflowmetry device until they have received specific direction to use it during the post-urodynamics safety phone call. The patient will then drop the device back to the GP Practice within two weeks. If the patient is unable to do this, they will be provided with packaging to post the device back within two weeks.

### **3 Day Follow Up Phone Call**

[figure not shown]
Research nurses performing the urodynamics reference test will be responsible for conducting a follow up phone call to the patient 3 days following the procedure. The research nurse will be required to complete the corresponding 3 Day Follow Up Phone Call CRF and work their way through the form with the patient, ensuring that any adverse event is documented. If the patient appears to have an infection, the research nurse should advise them to organise and attend a GP visit. If there is no indication of infection, research nurses will instruct the patient to begin using the uroflowmetry device.

## **Results**

Results from the uroflowmetry and urodynamics will be compiled and fed back to the GP via secure fax or email where the GP will be responsible for following up the patient as appropriate. Guidance on further management and treatment decisions will be provided to GPs, but the clinical management of the patient is at the discretion of their treating clinician.

The participants' NHS medical notes will be reviewed at approximately 3-6 months post assessment to record the clinical management and treatment decisions.

## **11.1 Training of Staff**

All staff involved in the study specific procedures (including recruitment/consent, collection of study data, application of intervention and clinical assessments) will be trained in the relevant aspects of GCP.

All relevant staff at sites will receive training to ensure they understand the PriMUS study protocol and how to identify potential participants. All staff at each site with delegated responsibilities for any aspect of the PriMUS study will be provided suitable training to ensure they understand the study procedures.

Clinicians responsible for making management decisions will be given guidance and training on the clinical management scenarios, but will be free to manage the patient using their own clinical judgement.

Research Nurses involved in performing urodynamics will be required to have sufficient clinical and study training. They will preferably have completed a recognised urodynamic course (e.g. <https://www.nbt.nhs.uk/bristol-urological-institute/bui-education/certificate-urodynamics-course>).

Each of the three research hubs will have a urology ‘champion’ who will be available during the period of the study to answer any urgent clinical queries following the urodynamic procedure. Throughout the study there will be an element of peer support offered by members of the study clinical team.

All urodynamic training will be overseen by the urologists and personnel will be signed off once deemed fully trained. A researcher manual will be provided, which will document the study-specific processes in detail, including full instructions of how to use the equipment. Upon completion of this training, personnel should file relevant proof of training and certificates into the site file.

Sites will receive a full training manual, which will document all study-specific processes in detail, which will be used as part of the site initiation training.

## **11.2 Clinical Assessments /Data Collection**

For men who are willing and consent to participate, results of the required index and reference tests will be recorded as they are performed. This will be co-ordinated by the research nurse for the study at each hub aided by primary care records and Research Network support. GPs will complete the Patient Eligibility Checklist, which will confirm that the patient is eligible to enter the study. The results of these tests will not be detailed on the Patient Eligibility Checklist. Data collected from the index tests performed by the GP during the first GP consultation will be documented on the Patient Eligibility

Results form. The potential participants will be required to complete and sign a Consent to Contact Form, confirming that they are happy to be contacted by the research nurse and giving permission for their medical records to be reviewed, so that research nurses can follow up any results of the index tests that aren't readily available immediately following the initial GP consultation (i.e. PSA test).

The results of the tests will be compiled into a results report form, which will subsequently be sent to the GP for further symptom management. The study research nurse performing the urodynamics will not have knowledge of all the results of the index tests when performing and analysing the reference test, only those needed to inform the urodynamic procedure.

As detailed in Table 2 below, the minimum dataset will comprise: age (years), bladder exam (palpable/not palpable), digital rectal exam (mild/moderate/severe enlargement), PSA ( $\geq 1.5$  pg/mL or  $< 1.5$  pg/mL) and as an absolute value, symptom score with storage, filling and QoL components, uroflowmetry ( $Q_{\max}$  in mL/s and  $V_{\text{void}}$  in mL), residual volume (mL), frequency volume chart [Waking (day) time frequency, sleeping (night) time frequency, 24 hour voided volume, average voided volume, nocturnal voided volume]. The variables from urodynamics will include a 3-item quality control checklist; zeroed to atmospheric pressure, adequate subtraction of abdominal pressure and detrusor pressure starting at zero ( $\pm 5$  cmH2O), detrusor overactivity on filling (Yes/No), BOOI ( $> 40$  or  $\leq 40$ ), BCI ( $< 100$  or  $\geq 100$ ), and absolute values for both BOOI and BCI.

Table 2		Initial GP Consultation		Study Visit (Either 1 Visit or 2 Separate Visits)	
Procedures	Description and Documentation	Screening	Baseline	Part 1 (Consent, Questionnaires and home tests, and Remainder of Index Tests, if not performed at GP visit)	Part 2 (Reference Test Urodynamics)
Patient Documentation and Baseline CRF collection					
Eligibility assessment	Patients who patient with LUTS will be assessed by GP for eligibility	X			
Patient Information Pack	Patients who present at the GP with LUTS will be given a patient information pack, this includes the frequency volume chart	X			
Informed consent	Patients will be invited back to the site to give informed consent		(X)	X	
Index Tests and Flowmetry					
Demographics	Collection of demographical data including ethnicity			X	
Medical history	Your age, BMI, symptom duration, treatment history and any other relevant medical history will be recorded			X	
Physical Examination	An examination of your abdomen and genitals.		X		
Digital rectal examination	A gloved, lubricated finger will be inserted into patients back passage so that the prostate can be examined.		X		
*Prostate specific antigen blood (PSA) test	A test to measure the amount of prostate specific antigen in the blood. A raised level may be an indication of prostate cancer, but may also be due to non-cancerous enlargement or inflammation of the prostate.		X		
Frequency volume chart	A patient-completed/automated diary (at least 3 days) of the volumes and timing of urine passed.		X (Given in Patient Information Pack, completed at home)		

Uroflowmetry	Provided with a home flowmeter, for patients use at home: a measurement of urine flow rate and voided volume as a function of time using a simple meter.				X (Given in this visit, completed at home)
Post void residual	Simple abdominal ultrasound scan to determine the volume of urine remaining in the bladder after urination.				X
Questionnaires					
ICIQ-Male LUTS* symptom questionnaire	Patient-completed validated questionnaire which defines presence, type and severity of LUTS			X	
IPSS questionnaire	Patient-completed validated questionnaire which defines presence, type and severity of LUTS			X	
Reference test					
**Urodynamics	This is the most invasive test involved in the study and carries a small risk of a bladder infection (under 'Expected Adverse Events From Urodynamics' details below), but it also gives the best information about what is causing the urinary symptoms.				X
*PSA test – within the previous 6 months prior to baseline visit					
**Urodynamics – within the last 6 months (providing the data meets the Quality Control 3 – item checklist within our specification)					

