The GP will complete the Digital Rectal Examination (DRE), Prostate Specific Antigen (PSA) Test and the Physical Examination, (as outlined in NICE clinical guideline CG97) and complete the eligibility checklist, confirming the patient is eligible to enter the study. The GP will also be required to record the results from these tests on a separate eligibility results form. At the study visit with the research nurse, the study will be explained in more detail and the research nurse will establish whether or not the patient wishes to take part. Those who are happy to enter and are eligible will be asked to provide informed consent.

During this appointment, the patient will complete the ICIQ Male LUTS symptom questionnaire and the IPSS questionnaire. The research nurse will complete the patient registration CRF, which will include data collection for the remaining study index tests (i.e. medical history and demographics).

If possible, the research nurse will arrange for the participant to undergo the reference test of (urodynamics) at the same study visit to minimise patient burden, however, in some circumstances this may take place as two separate study visits. This will preferably be performed by the research nurse at the GP practice but with access to the local urology service if required. In some circumstances the urodynamics may take place in a secondary care setting.

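### Masking of the nurse who reads urodynamics is partial, undefined and hard to keep in the written workflow, which leaves the detrusor overactivity reading open to review bias

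*Protocol*

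**What the plan says.** Section 11.2 states the masking rule. The nurse performing urodynamics "will not have knowledge of all the results of the index tests when performing and analysing the reference test", with the exception "only those needed to inform the urodynamic procedure". The protocol does not say which results fall under that exception.

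The workflow around the rule is as follows:

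- On the recording of index and reference results, section 11.2 says "This will be co-ordinated by the research nurse for the study at each hub aided by primary care records and Research Network support".
- The ICIQ and IPSS are completed by the patient at the research nurse's appointment (9.1; section 11, Part A). Part A adds: "The research nurse will complete the remaining index tests by completing the corresponding CRFs". Section 9.1 narrows these remaining tests to medical history and demographics.
- The nurse tells the patient how to complete the frequency volume chart, which is due before Part A (section 11).
- Section 11.2 gives the purpose of record review: "research nurses can follow up any results of the index tests that aren't readily available immediately following the initial GP consultation (i.e. PSA test").
- If possible, "the research nurse will arrange for the participant to undergo the reference test of (urodynamics) at the same study visit", and it is preferably the research nurse who performs it (9.1). Two separate visits are also allowed.

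Section 10.3 defines DO by a "phasic (transient) detrusor pressure rise during bladder filling associated with a sensation of urgency", and 11.2 records it as Yes or No. Bladder outlet obstruction (BOO) and detrusor underactivity (DU) are defined by fixed cut-offs on two indices. Section 10.4 plans expert review of a sample of urodynamic tests and does not say whether the reviewers are masked.

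**The concern.** The primary outcome (5.3) is the sensitivity and specificity of a model built from the index tests, judged against urodynamics. If the person reading the reference test already knows the predictors, borderline readings can drift towards what the predictors suggest. Apparent agreement then rises without any gain in true accuracy.

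The protocol recognises the risk by stating a masking rule. The rule depends on an undefined exception, and most of the index information passes through the person it is meant to mask. Adherence cannot be checked, because no list says what the nurse was allowed to see. Lost masking cannot be repaired at analysis short of masked re-reading of the traces.

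**Working it through.** The protocol gives no figure for masking, so the check is a tracing exercise, followed by an illustration on assumed values.

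**Step 1. Trace each index test in Table 1.**

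| Index test | How it is obtained | Within the nurse's reach before the trace is read? |
|---|---|---|
| Age | Nurse's registration form (9.1) | Yes |
| ICIQ | Patient-completed at nurse appointment | Yes |
| IPSS | Patient-completed at nurse appointment | Yes |
| Frequency volume chart | At home, due before Part A | Yes |
| Post void residual | Part B, the urodynamics visit | Yes, with the caveat below |
| PSA | GP; nurse may follow up if outstanding | Only if chased |
| Abdominal examination | GP, separate results form | Normally no |
| Digital rectal examination | GP, separate results form | Normally no |
| Home uroflowmetry | After the 3-day call that follows urodynamics | No |

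Count: 5 yes + 1 conditional + 2 normally no + 1 no = 9. So 5 to 6 of 9 are within reach.

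Two caveats apply. The protocol does not say who scans the residual, and 10.3 places a residual measurement at the end of urodynamics. If that is the index measurement, it is known when the trace is analysed but not during filling, and the count at filling is 4 to 5. The two GP examinations are marked normally no because the Part 1 column heading of Table 2 allows index tests not done at the GP visit to be done at the study visit.

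**Step 2. Which target is exposed.** BOO requires an index above 40 and DU an index below 100, both computed from values read off the recording. DO has no numeric threshold: someone decides whether a pressure rise is phasic and goes with urgency. The questionnaires available at the same visit include a storage symptom score, which is a candidate predictor. DO is also the commonest target, at 57% (section 4).

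**Step 3. Would validation show it?** The protocol describes one procedure for both cohorts (6.1, section 11). A reading habit in the development cohort can recur in the validation cohort, so good validation performance would not rule it out.

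**Step 4. Size, as an illustration only.** Take the validation cohort of 325 and DO prevalence of 57% from the protocol: 325 × 0.57 = 185.25 and 325 × 0.43 = 139.75, which match the 185 and 140 in section 16.1. Take true sensitivity and specificity of 75%, the planning value. Assume that a fraction f of discordant men have the reference reading moved to agree with the index impression, and that this impression matches the model's classification. The documents give no value for f.

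- Starting cells: TP = 138.94, FN = 46.31, TN = 104.81, FP = 34.94.
- After the shift: TP′ = TP + f·FP, FN′ = (1 − f)·FN, TN′ = TN + f·FN, FP′ = (1 − f)·FP.
- For f = 0.10: sensitivity = 142.43 / (142.43 + 41.68) = 0.774; specificity = 109.44 / (109.44 + 31.44) = 0.777.

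| f (assumed) | Apparent sensitivity | Apparent specificity |
|---|---|---|
| 0 | 0.750 | 0.750 |
| 0.05 | 0.762 | 0.763 |
| 0.10 | 0.774 | 0.777 |
| 0.20 | 0.798 | 0.803 |

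**The case against.** A reader might infer that the stated blinding does not exist, that the nurse knows nearly all the index results, or that only home flow is unknown. The documents do not support this. Section 11.2 claims only partial masking, with an express exception. Part of it works: home flow is measured after urodynamics, and the GP's results go on a separate form and are kept off the eligibility checklist. PSA follow-up applies only when the result is outstanding. Testing at a single visit is conditional on its being possible, and no frequency is given.

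Handling a patient-completed questionnaire is also not the same as scoring it, and nothing says that the scores are worked out before the trace is read. Urgency in the DO definition is a sensation observed during filling, not a questionnaire score. The researcher manual may hold further detail that is not shown here.

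The illustration is also open to challenge. The value of f is assumed, and no model exists when the development traces are read. The model may also use predictors other than symptoms, so the nurse's impression and the model's output will not coincide. The shifts of about 1 to 5 points lie within the 8-point precision that section 16.1 states for DO.

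All of these limits stand. They narrow the point without removing it: the permitted results are not listed, nothing shown prevents scoring before reading, and the 10.4 review covers a sample with no masking stated. A systematic shift is also not something that a confidence interval accounts for.

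**Conclusion.** The point holds in a limited form. Masking of the reference reader is partial and undefined, and the written workflow puts about 5 to 6 of the 9 index tests within that reader's reach before the trace is read. DO is the target most exposed. BOO and DU are less so, although their traces still have to be read. Because both cohorts use the same procedure, validation would not reveal the bias; the documents do not show that it would be equal in both.

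The size cannot be derived from the protocol. The illustration shows direction and a plausible scale under an assumed f, and is not an estimate. The conclusion rests on the workflow being followed as written, with the same nurse in both roles as the protocol prefers. It is a worthwhile and inexpensive improvement, not a fatal flaw.

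**What to change.** 1. In section 11.2, list which index results the nurse may see before urodynamics.
2. Have the patient seal the ICIQ and IPSS or enter them directly, and leave them unscored until the reading is done.
3. Require the DO call and the pressure-flow readings to be locked in the web-based CRF before the other index CRFs are opened, including the GP results form and PSA.
4. Make the trace reviews already planned in 10.4 masked to index results, and report agreement on DO in that sample. The sample cannot mask the reference standard for the whole cohort, but it gives some evidence on the DO readings.

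PSA follow-up can stay with the nurse if it is done after the lock, so the consent wording on record review need not change. The GP's checklist already conveys eligibility without the values. The cost is CRF ordering, a way of sealing the questionnaires, and short additions to the researcher manual and monitoring plan, with slightly more form handling at the visit. No extra staff or procedures are needed.
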